4.1. Control Group

4.1.1. Summary: Received an autonomous preoperative rehabilitation exercise programme.

4.1.2. Method: On the day of admission, a research assistant provided a verbal explanation of the preoperative rehabilitation exercise regimen and distributed a guidance manual. Participants are advised to perform autonomous exercises 2–3 times daily according to the manual from admission day to surgery day (preoperative). They were also advised to promptly inform ward medical staff of any unusual conditions or concerns.

4.1.3. Preoperative rehabilitation exercise regimen

A. Exercises for pulmonary function:

- a) Abdominal breathing: 10 sets per time, 2-3 times per day.
- b) Effective coughing: Practice repeatedly until mastered.

B. Exercises for quadriceps Strength:

- a) Straight leg raise: Alternate legs, 10 sets per time, 2-3 times per day.
- b) Lateral leg raise: Alternate legs, 10 sets per time, 2-3 times per day.

C. Exercises for the knee range of motion:

- a) Knee flexion: Alternate legs, 10 sets per time, 2-3 times per day.
- b) Knee extension: Alternate legs, 10 sets per time, 2-3 times per day.

D. Exercises for preventing lower limb thrombosis:

- a) Ankle pump exercise: Both feet simultaneously, 10 sets per time, 2-3 times per day.

4.2. Experimental Group

4.2.1. Summary: Received a patient-navigation-based preoperative rehabilitation exercise programme

4.2.2. Method: From admission day to surgery day (preoperative), navigator provided full-period preoperative rehabilitation exercise guidance and navigation services aimed at promoting rehabilitation exercise.

A. The navigator provided full-period preoperative rehabilitation exercise guidance, which displayed as follows: (The preoperative rehabilitation exercise regimen guided by the navigator was the same as that of the control group.)

- a) On the day of admission, in addition to explaining the preoperative exercise regimen and distributing a guidance manual as done for the control group, the navigator demonstrated the exercise movements and required participants to

perform return demonstrations to ensure mastery of the exercises.

- b) During the preoperative period, navigators conducted daily ward visits to provide face-to-face exercise guidance, including two 20-minute supervised sessions per day, and sent exercise reminder text messages every night from 7:00 PM to 8:00 PM.

B. The navigation services aimed at promoting rehabilitation exercise encompassed the following seven themes: On the day of admission, (i) establish contact with participants or their carers, and (ii) provide disease-related education. During the preoperative exercise period, (iii) assess participant needs and facilitate access to resources; (iv) offer social and emotional support; (v) provide verbal interpretation services

available upon request; (vi) identify and address barriers to exercise implementation; and (vii) support participants' self-management.

(i) Establish contact with participants or their carers: On the day of admission, the navigator will add the participant's or their carer's contact details and inform them that they may consult the navigator via these contact details should they have any queries or requirements during the preoperative rehabilitation exercise period.

(ii) Provide disease-related education:

- ① Knee Osteoarthritis Information: Including the definition of osteoarthritis, the development of knee osteoarthritis, and the grading of knee osteoarthritis.
- ② Total Knee Arthroplasty Surgery Information: Surgical method and benefits of the surgery.
- ③ Perioperative care guidance: Including preoperative daily life precautions, management of perioperative pain, respiratory care, postoperative lower limb thrombosis prevention, and preparation of surgical supplies.

(iii) Assess participant needs and facilitate access to resources:

- ① Needs assessment: Navigators will understand participants' illness conditions, prior treatment histories, and current physical states and will discuss expectations regarding the surgery with participants, which includes pain management, functional recovery, and quality-of-life improvements, alongside anticipated post-operative rehabilitation requirements such as physiotherapy, independence in activities of daily living, and care support.
- ② Resource linkage: Based on the needs assessment, the navigator

will introduce available hospital resources to participants, such as rehabilitation and pain management teams, the hospital's psychological counseling centre, and continuing care services.

- ③ Information provision and assistance: The navigator will explain the surgical procedure, post-operative precautions, and expected recovery timeline in detail according to the participant's needs, ensuring they understand each step. Information on hospital companion services will be provided, including details of companions, contact information, service content, and fees. Offer medical insurance reimbursement details, with navigators explaining coverage scope, claim procedures, and consultation channels for different insurance schemes. Additionally, navigators will assist with scheduling appointments for specialised examinations or treatments.
- ④ Reminder services: Navigators will provide reminders for scheduled preoperative examinations, including advance notification of any special requirements (e.g., fasting, holding urine). Navigators will also offer weather-related reminders and guidance as appropriate.

(iv) Offer social and emotional support:

- ① Provide encouragement and support: During preoperative rehabilitation exercises, navigators offer positive feedback and encouragement to help participants build confidence and overcome psychological barriers. Sharing video testimonials of successful recovery cases inspires participants' motivation to exercise; using quantifiable metrics (such as scales) to document progress enables participants to perceive the effects of rehabilitation.
- ② Provide psychological counseling: Should participants exhibit negative emotions such as anxiety or depression, navigators

promptly offer psychological support, providing effective coping strategies and encouraging participants to express their feelings to aid emotional regulation.

- ③ Encourage family or carer involvement: Encourage family members or carers to actively join in the participant's rehabilitation exercises and active communication with participants, and jointly provide support and reassurance to participants.

(v) Provide verbal interpretation services available upon request: navigators can provide participants with verbal interpretation services in Cantonese, Mandarin, and Teochew.

(vi) Identify and address barriers to exercise implementation:

- ① Lack of interest or motivation in exercise: Explain the purpose and benefits of preoperative rehabilitation exercises; actively share success stories of preoperative rehabilitation exercises; provide positive feedback and encouragement.
- ② Negative emotional impact: Offer timely psychological counseling, encourage participants to express their feelings, and assist in emotional regulation; teach participants relaxation techniques (such as meditation and deep breathing) to alleviate stress; and encourage mutual support and communication among participants.
- ③ Failure to perceive anticipated outcomes: Utilise quantifiable knee metrics (e.g., knee function scales, pain scales, etc.) to document participant progress; conduct daily exercise progress reviews with participants and adjust preoperative rehabilitation programmes based on feedback.
- ④ Fear of pain: Inform participants about normal pain thresholds during rehabilitation exercises and provide pain relief strategies; guide participants to perform preoperative rehabilitation exercises at an intensity tolerable to them; Inform participants that a rehabilitation navigator will provide ongoing guidance in the ward.

- ⑤ Limitations due to comorbidities: Measures as per (vii)② below.
- ⑥ Insufficient family and carer support: Measures as per (iv)③ above.
- ⑦ Weather impediments: Provide participants with considerate reminders and rehabilitation exercise guidance based on weather conditions.

(vii) Support participants' self-management:

- ① Perioperative safety guidance: Inform participants of safety precautions when using walking aids, fall prevention measures, and safety considerations for using medical facilities and equipment.
- ② Guidance for participants with underlying conditions: Upon admission, navigators conduct detailed assessments of participants' underlying conditions, collaborating with the medical team to develop personalised management plans. Participants receive instruction on monitoring relevant indicators and operating associated devices, adhering to medication schedules as prescribed, managing daily lifestyle factors (diet, exercise, weight control), and recognising and handling emergencies or abnormal symptoms.
- ③ Postoperative self-management guidance for TKA:
 - Wound care: Explain dressing change schedules, precautions during dressing changes, and wound dressing observation.
 - Complication prevention: Instruct on preventing postoperative wound infections, deep vein thrombosis, and constipation.
 - Postoperative life precautions: Inform on prohibited movements, allowed actions, and mobility techniques.

5. Data collection

Data collection will be conducted at five time points: on admission day (baseline, T0), surgery day (preoperative) (T1), one week post-surgery (T2),

two weeks post-surgery (T3), and four weeks post-surgery (T4). The collected study data will include demographic and clinical information collected by the principal investigator (recruiter), as well as outcome measures collected by assessors from T0 through T4. These outcome indicators encompass knee osteoarthritis severity, exercise adherence, self-efficacy, knee joint function, knee range of motion, and pain intensity.

6. Outcome assessment

6.1. Primary outcome

The primary outcome is the change in knee osteoarthritis severity from admission day (baseline, T0) to surgery day (preoperative) (T1). As the intervention in this study aims to enhance patient adherence to preoperative rehabilitation exercises, the ultimate objective is to improve their rehabilitation outcomes. Therefore, the change in knee osteoarthritis severity from T0 to T1 in both groups of participants will be used to evaluate the effectiveness of the intervention.

Knee osteoarthritis severity will be measured using the Chinese version of the Western Ontario and McMaster Universities Osteoarthritis Index (WOMAC) Scale, which is a self-administered instrument specifically developed to assess the severity of knee osteoarthritis and the efficacy of related treatments (Bellamy et al., 1988). The scale consists of 24 items divided into three subscales: pain (5 items), stiffness (2 items), and physical function (17 items). Several scoring methods have been developed for the Western Ontario and McMaster Universities Osteoarthritis Index Scale items (Noyes, 2016). In this study, a 5-point Likert scale is employed, where 0 represents “no difficulty” and 4 represents “extreme difficulty”. The total score ranges from 0 to 96, with higher scores reflecting more severe knee osteoarthritis.

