2.1. Participant selection criteria

Inclusion Criteria: (i) patients diagnosed with knee osteoarthritis who are undergoing primary unilateral total knee arthroplasty; (ii) aged between 45 and 90 years; (iii) assessed by the attending physician as having sufficient physical capacity to tolerate preoperative rehabilitation exercises and adequate communication skills to cooperate with all examinations and assessments; and (iv) informed consent was obtained from the patient, and the signed informed consent form was duly completed.

Exclusion Criteria: (i) patients who are uncooperative due to impaired consciousness, cognitive dysfunction, or other factors; (ii) presence of severe concurrent comorbidities, including liver cirrhosis, respiratory failure, renal failure, malignancy, or trauma; (iii) a history of significant neuromuscular disorders or other joint diseases, as determined by the attending physician, that impair knee joint function; (iv) a time interval of greater than 7 days or less than 3 days between the admission day date and the scheduled surgery date; and (v) patients who have undergone systematic lower limb functional training within the past four weeks.

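### The primary T1 assessment exists only if surgery takes place: the plan has no rule for cancelled or moved operations, and it does not use the scheduled 3 to 7 day interval in the analysis

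*Combined protocol and SAP*

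**What the plan says.** Two different dates are in use.

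- **Eligibility.** Section 2.1 excludes patients with "a time interval of greater than 7 days or less than 3 days between the admission day date and the scheduled surgery date". This is a single check at entry, on the scheduled date.
- **Primary endpoint.** Section 6.1: "The primary outcome is the change in knee osteoarthritis severity from admission day (baseline, T0) to surgery day (preoperative) (T1". Section 5 hangs the later visits on the same event: "surgery day (preoperative) (T1), one week post-surgery (T2", and so on to T4. No study day, visit window or fallback is given for T1.
- **Exposure.** Section 4.2.2: "From admission day to surgery day (preoperative), navigator provided full-period preoperative rehabilitation exercise guidance". Section 4.1.2 gives controls the same start and end for autonomous exercise. Exercise time therefore moves with the operation in both arms.
- **Moved or cancelled surgery.** It is not among the withdrawal reasons in section 9.1. Section 7 covers all randomised participants and has one general missing-data rule: GEE alone below 5% missing, multiple imputation otherwise.
- **Use of the interval.** Section 3 names no stratification factor, and section 7 names no covariate for days from admission to surgery.
- **Services in the experimental arm only.** Under section 4.2.2 B, "navigators will assist with scheduling appointments for specialised examinations or treatments"; "Navigators will provide reminders for scheduled preoperative examinations"; and, for underlying conditions, navigators assess patients, "collaborating with the medical team to develop personalised management plans".

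**The concern.** The primary outcome is a self-completed questionnaire about the period before surgery. Nothing in its content needs the operation to happen, but its definition does. If surgery is cancelled there is no surgery day, so T1 is undefined, and T2 to T4 are undefined with it. A patient may be cancelled because of a health problem found during the work-up, and such a patient may also differ in WOMAC change. The trial would then lose primary outcomes selectively, when a visit by the existing assessor could have kept them.

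If surgery is moved, T1 is still obtained, but the interval can fall outside the 3 to 7 days that the entry criterion was meant to secure. Even when nothing moves, the interval varies more than twofold between patients and fixes how much exercise each can do before T1. It is known before allocation, and the analysis leaves it unused.

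**Working it through.** **1. The plan's own figure.** Section 2.2 gives 33 per group, 20% attrition and 84 in total. The attrition step reproduces: 33 / (1 − 0.20) = 41.25, rounded up to 42 per group and 84 overall. The 33 itself does not follow from an effect size of 0.8, power 0.80 and two-sided alpha 0.05: 2 × (1.960 + 0.842)² / 0.8² = 24.5, so 25 per group, or 26 by the t-test. That is a separate matter. It makes the trial larger than its stated inputs need and does not alter this point.

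**2. Following three patients through the text.**
- Surgery on the scheduled date: T1 is defined, and the interval is 3 to 7 days.
- Surgery moved: T1 is defined, but the interval may be shorter than 3 or longer than 7 days. No rule says whether the value is in or out of window.
- Surgery cancelled: T1 to T4 are undefined and only T0 exists. Section 7 still counts the patient as analysed, but imputation would have to fill in a surgery-day value for someone who has no surgery day.

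**3. How many could be lost.** The documents give no cancellation rate. Assuming 5% to 10%: 0.05 × 84 = 4.2 and 0.10 × 84 = 8.4, so about 4 to 8 participants. If the 5% rule in section 7 is counted as participants without T1 (the plan does not say), 4/84 = 4.8% stays below it and 5/84 = 6.0% crosses it. Below the threshold the plan relies on GEE alone, and an unweighted GEE generally needs missingness to be unrelated to outcome.

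**4. Power.** Two-sample t-test, effect size 0.8, two-sided 0.05:

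| T1 lost | n per group | Power |
|---|---|---|
| 0% | 42 | 0.952 |
| 5% | 39 | 0.937 |
| 10% | 37 | 0.924 |
| 20% | 33 | 0.893 |

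Power is not at risk at any plausible loss.

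**5. Selective loss.** If a share p of one arm has no T1, and those patients' mean change differs by δ from that of the rest of the arm, the observed mean is off by p × δ from the mean over everyone randomised to it. As an illustration, put all losses in one arm, p = 0.05 to 0.10, and let δ be as large as the planned effect, 0.8 SD. The bias is then 0.05 × 0.8 = 0.04 SD to 0.10 × 0.8 = 0.08 SD, which is 5% to 10% of the planned effect. Both p and δ are assumptions.

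**6. Exercise time within the window.** Section 4.2.2 gives two 20-minute supervised sessions a day. Counting one pair per day of interval: 3 × 2 × 20 = 120 minutes and 7 × 2 × 20 = 280 minutes, a ratio of 2.33. Controls, at 2 to 3 times daily, would be advised 6 to 9 bouts over 3 days (3 × 2 to 3 × 3) and 14 to 21 over 7 days (7 × 2 to 7 × 3). This is variation between patients, set before allocation. It is not a difference between arms.

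**7. Arm difference in timing.** Its effect would be the daily change in WOMAC times the difference in mean days to T1. The documents supply neither quantity, so I give no figure.

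**The case against.** The strongest reply concerns the link from allocation to timing. A reader might infer that navigators, by helping with appointments and reminding patients of examinations, keep surgery on schedule in one arm and so distort the primary contrast. The documents do not show this. No sentence gives navigators a part in setting or moving the surgery date. The appointment help is assistance according to the patient's needs. The preparation notices concern examinations, not the operation. Nothing says that controls, who are inpatients on the same ward, lack work-up support. If timing did change, one could fairly call it part of the programme's effect, since both arms' exercise is defined to end on surgery day. If controls waited longer and exercise helps, the difference would shrink, which does not favour a false claim of superiority. That reply stands: an effect of allocation on timing is possible in principle, with size and direction unknown.

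It is also fair that the twofold range in exercise time is balanced in expectation by randomisation, so ignoring it costs precision and not validity. And cancelled patients are not simply dropped: section 7 keeps all randomised participants, section 2.2 allows for 20% attrition, and the clinician-judged withdrawal in section 9.1 might cover some health-related cancellations.

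Two gaps survive this. Imputation and an attrition allowance do not say what T1 means for a patient without surgery, nor do they justify losing a value that could be collected. And a prognostic value already recorded for eligibility is left out of the analysis without a reason.

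Moving T1 to the scheduled date for everyone would go too far. It would change the target for postponed patients, whose programme is still running, and T1 would still move when surgery is brought forward.

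**Conclusion.** The point holds in this form. Eligibility uses the scheduled date, T1 exists only on the actual surgery day, and the plan is silent on surgery that is cancelled or moved. Cancelled patients have no defined primary outcome although it could be measured. Patients whose surgery is moved can be measured outside the window. The scheduled interval is unused.

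The gap in the text is certain; its consequence is probably modest. At an assumed 5% to 10% cancellation, 4 to 8 participants are affected and power stays above 0.92. The bias reaches 0.04 to 0.08 SD only if all losses fall in one arm, at 5% to 10% of that arm, and those patients differ by a full 0.8 SD. The documents do not support the stronger conclusion that the primary contrast is confounded by navigator-driven timing. Reporting intervals by arm would let readers judge that.

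**What to change.** 1. Record the scheduled surgery date before the envelope is opened.
2. Keep T1 on surgery day wherever surgery goes ahead. For any participant whose surgery is postponed or cancelled, also collect the WOMAC on the recorded scheduled date. Use that value as T1 if surgery does not take place, and in a sensitivity analysis if it is postponed. State when a postponed operation counts as not having taken place.
3. Add the scheduled interval in days as a covariate in the primary comparison. Use the scheduled interval, because the actual one arises after randomisation. In a model of the T0 to T1 change a main effect is enough; in a GEE with T0 among the responses it needs a term with time, or it will not bear on the change.
4. Report the actual T0 to T1 interval, postponements and cancellations by arm.

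Cost: protocol wording, one recorded date, and a few extra questionnaires by the existing assessor, some possibly after discharge. The drawback is that T1 for cancelled patients is not a surgery-day value, which the report should say. If data collection is already complete, items 3 and 4 remain possible wherever both dates were kept.

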6.2. Secondary outcomes

The secondary outcomes are changes from baseline in exercise adherence, self-efficacy, knee joint function, knee range of motion, and pain intensity at T1, T2, T3, and T4, as well as changes from baseline in knee osteoarthritis severity at T2, T3, and T4.

Exercise adherence will be measured using the Orthopaedic Patient Functional Exercise Compliance Scale developed by Chinese scholars (Tan et al., 2019). This instrument effectively assesses rehabilitation adherence among orthopaedic patients. It consists of 15 items covering three dimensions—physical exercise adherence, psychological exercise adherence, and active learning exercise adherence—with patients rating their ability to perform each activity. Each item is rated on a five-point Likert scale ranging from 1 (“Not at all possible”) to 5 (“Completely possible”). Total scores range from 15 to 75, with higher scores reflecting greater adherence to rehabilitation exercises.

Self-efficacy will be measured using the Chinese version of the Self-Efficacy for Rehabilitation Scale (SER) (Wang et al., 2014). This scale has demonstrated strong reliability and validity in assessing rehabilitation self-efficacy among patients undergoing knee replacement. The Chinese version of the Self-Efficacy for Rehabilitation Scale includes two dimensions—Rehabilitation Self-Efficacy (five items) and Coping Self-Efficacy (seven items)—for a total of 12 items. Each item is rated on an 11-point Likert scale ranging from 0 (“Not at all”) to 10 (“No difficulty whatsoever”), yielding a maximum total score of 120. Higher scores denote greater rehabilitation self-efficacy.

Knee joint function will be measured using the Hospital for Special Surgery (HSS) Knee Scoring System (Weitzel et al., 2002). This 100-point scoring system includes pain (30 points), function (22 points), range of motion (18 points, one point per eight degrees), muscle strength (10 points), flexion

deformity (10 points), and stability (10 points). Points are deducted if patients use walking aids or present with flexion contracture or varus/valgus deformities. Total scores range from 0 to 100, with higher values reflecting superior knee joint function.

Knee range of motion (ROM) will be measured with a goniometer. ROM measurement assesses knee movement amplitude, serving as a critical indicator of knee joint function and a key indicator for evaluating rehabilitation outcomes following total knee arthroplasty. Normal knee range of motion values are as follows: flexion, 0°–135°; extension, 0° (some individuals may exhibit hyperextension of 0°–10°); active range, 0°–135°; and passive range, up to 150°.

Pain intensity will be measured using the Visual Analogue Scale (VAS). The VAS consists of a 10-centimetre horizontal line divided into 10 equal intervals, where higher scores represent greater pain intensity. A score of 0 denotes no pain, whereas a score of 10 denotes the most severe pain imaginable. Patients are instructed to mark the point on the line corresponding to their perceived pain intensity.

7. Statistical analysis

IBM® SPSS Statistics 27.0 will be used to analyse the data from all randomised participants. Statistical significance was set at $p \leq 0.05$. Categorical variables (e.g., gender, marital status, payment type) appeared as frequencies and percentages. Continuous variables (e.g., age, height, weight) appeared as mean \pm standard deviation (SD). Continuous data meeting the assumptions of normality and homogeneity of variance were analysed using independent-sample t-tests; otherwise, the Wilcoxon signed-rank test appeared. Categorical data were analysed using the chi-square test or Fisher's exact test for intergroup comparisons. Generalised Estimating

Equations (GEE) were employed to compare longitudinal changes in outcome variables between groups, with statistical significance set at $p < 0.05$ (two-tailed). The GEE was chosen as it accounts for within-subject correlations inherent in repeated measures, thereby improving the efficiency of parameter estimation in longitudinal analyses. Moreover, the GEE approach flexibly accommodates missing data. When the proportion of missing data was below 5%, the GEE inherently accommodated the missing values; otherwise, multiple imputation procedures were applied.

8. Trial monitoring

The Clinical Research Management Department and the Ethics Committee of the study-conducting hospital will oversee trial implementation and ensure compliance with ethical standards. The principal researcher is required to submit regular progress reports and interim results to the Clinical Research Management Department and the Ethics Committee of the study-conducting hospital. They will review the completeness, accuracy, and timeliness of data collection, as well as procedures related to participant enrolment, informed consent, eligibility assessment, and protocol adherence. Based on the findings of interim reports and a comprehensive evaluation of the study's efficacy, safety, and feasibility, they will make the final determination regarding whether the trial should be terminated.

9. Ethical

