2.2. Sample size

This study used knee osteoarthritis severity as the primary outcome measure. Given the lack of prior research on the effect of patient navigation mode on patients' knee osteoarthritis severity. Therefore, the sample size calculation for the present study was based on the results of the pre-experiment, which showed an effect size of 0.8 on knee osteoarthritis severity. To achieve a statistical power of 0.80 and an alpha level of 0.05, a sample size of 33 participants per group is required. Considering a 20% attrition rate, the total estimated sample size is 84 participants, with 42 participants per group.

3. Randomization and blinding

A non-research team member randomly selected an initial starting point from a pre-generated computerised random number table. From this point, the corresponding random numbers were sequentially identified, ranging from 1 to 84. After sorting the random numbers, participants were randomly assigned in a 1:1 ratio to either Group 1 (the experimental group) or Group 2 (the control group). Group assignments were concealed within 84 consecutively numbered, identical, opaque, and sealed envelopes, which the non-research team member securely kept. On the day of participant enrolment, after completing demographic and clinical data collection, as well as baseline assessments, the principal researcher (recruiter) retrieved the envelope corresponding to the participant's sequential number from the custodian. The envelope was opened, and the participant was assigned to the designated group.

Due to the nature of the intervention, the experimental group received exercise guidance from navigator, while the control group did not. Consequently, blinding of participants, recruiters, or research intervention staff was not feasible. However, outcome assessors and data entry analysts will be blinded. The outcome assessor is an independent research assistant who remained unaware of the allocation status throughout the study. Before the

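### Exercise adherence is compared as change from a T0 score taken before the regimen is given, with no baseline covariate named; adjusting for T0 would be at least as precise at no cost

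*Combined protocol and SAP*

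**What the plan says.** Section 6.2 reads: "The secondary outcomes are changes from baseline in exercise adherence, self-efficacy, knee joint function", followed by range of motion and pain, each at T1, T2, T3 and T4. Adherence is a 15-item self-rated total from 15 to 75. Section 5 places T0 on admission day and T1 on the day of surgery, before the operation.

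Section 3 fixes the order of events on enrolment: "after completing demographic and clinical data collection, as well as baseline assessments, the principal researcher (recruiter) retrieved the envelope". The regimen comes as part of the allocated arm. For controls, Section 4.1.2 says: "On the day of admission, a research assistant provided a verbal explanation of the preoperative rehabilitation exercise regimen and distributed a guidance manual". Section 4.2.2 gives the experimental arm the same regimen, with the navigator's demonstration and daily supervision added. Section 2.1 excludes "patients who have undergone systematic lower limb functional training within the past four weeks".

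Section 6.1 states that raising adherence to the preoperative exercises is what the intervention is for. Section 7 compares longitudinal changes between groups by GEE. It does not list the model terms and mentions no baseline covariate.

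**The concern.** The T0 adherence score is given before the patient has received the programme that the later scores concern, and by a patient with no recent systematic lower-limb training. It may therefore predict adherence at T1 to T4 only modestly. A change score subtracts the whole of T0 whatever its predictive value. A covariate lets the data choose the weight.

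Adherence is the direct target of the intervention, so this comparison shows whether the navigator changed what it was meant to change. The trial is small (84 randomised, 33 per group assumed evaluable), so precision given up here could leave the result on mechanism unclear.

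**Working it through.** **Plan's own figure.** The documents give no SD, correlation, effect size or power for adherence, so there is nothing to reproduce. The 33 per group in Section 2.2 was set for WOMAC and serves here only as the number evaluable (33/0.8 = 41.25, rounded up to 42 per group, 84 in total).

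**Step 1: what the planned contrast is.** A GEE with group, visit and their interaction, and with T0 among the responses, was fitted to simulated complete data (33 per arm, five visits). The group-by-visit term at T1 was compared with the plain difference in mean change.

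- r = 0.1: 0.744 (SE 0.285) by both routes.
- r = 0.7: 0.936 (SE 0.200) by both routes.

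Independence and exchangeable working correlations gave the same answers. With complete data, GEE in this form recovers none of the precision lost by subtraction.

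**Step 2: variances.** Set the follow-up SD to 1, let k be the T0 SD as a multiple of it, and let r be the T0-to-follow-up correlation.

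- Follow-up score alone: 1
- Change from T0: 1 + k² − 2rk
- Adjusted for T0: 1 − r²
- Change minus adjusted: k² − 2rk + r² = (k − r)², which is never negative

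Apart from the small cost of estimating the slope, adjustment is therefore never less precise than change, whatever r and k are. With k = 1, the ratio of change to adjusted is 2(1 − r)/(1 − r²) = 2/(1 + r).

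**Step 3: numbers with equal SDs.** Power is for a two-sided 0.05 t-test at one visit, 33 per arm, true difference 0.5 follow-up SD. The 0.5 and every r are assumptions. Power for the follow-up score alone is 0.516 throughout.

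| r | Variance, change | Variance, adjusted | Ratio | Power, change | Power, adjusted |
|---|---|---|---|---|---|
| 0 | 2.0 | 1.00 | 2.00 | 0.293 | 0.516 |
| 0.2 | 1.6 | 0.96 | 1.67 | 0.353 | 0.533 |
| 0.3 | 1.4 | 0.91 | 1.54 | 0.394 | 0.555 |
| 0.5 | 1.0 | 0.75 | 1.33 | 0.516 | 0.637 |
| 0.6 | 0.8 | 0.64 | 1.25 | 0.609 | 0.706 |
| 0.8 | 0.4 | 0.36 | 1.11 | 0.885 | 0.915 |

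**Step 4: change against the follow-up score alone.** Change is noisier when 1 + k² − 2rk exceeds 1, that is, when r is below k/2. With equal SDs the threshold is 0.5. If T0 scores bunch (k = 0.5) it is 0.25, and the largest inflation for r of 0 or more is 1.25. At k = 0.5 and r = 0.3, change has variance 1 + 0.25 − 0.30 = 0.95, slightly below follow-up alone, while the adjusted variance is 0.91.

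**Step 5: does relabelling the outcome matter?** With T0 in a linear model, moving from level to change as the response shifts the T0 coefficient by exactly one and leaves the residuals untouched. A GEE on one simulated dataset confirmed that the group estimate and its standard error are the same either way. The gain comes from the covariate, not from the outcome's name.

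**The case against.** A reader might infer that T0 is an empty, hypothetical rating and that subtracting it must add noise. The documents do not support that.

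- **The scale.** Section 6.2 describes patients rating how able they are to do each activity, from not possible to completely possible. Such items can be answered before a regimen is given, and change in them can be interpreted. The items themselves are not in the documents. The exclusion covers systematic training only, not all exercise.
- **The correlation.** A low r is plausible but undocumented. At r = 0.6 with equal SDs, change beats the follow-up score alone (power 0.609 against 0.516), so the claim of added noise reverses.
- **The power figures.** They assume a 0.5 SD effect, one visit and full attrition, whereas Section 7 plans a repeated-measures analysis of all randomised participants. With 42 per arm and no loss, change gives 0.36 to 0.48 for r of 0 to 0.3, against 0.62 to 0.66 adjusted.
- **Scope.** Adjustment beats change for any outcome when SDs are equal and r is below 1, so the gap is partly a general one: the GEE terms are not specified.

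All four stand as limits. None favours subtraction over adjustment: if T0 is informative the covariate uses that information, and if it is not, the fitted weight shrinks towards zero.

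**Conclusion.** The point holds as a free improvement. The planned contrast for adherence is a difference in mean change, and adjusting for T0 is in large samples never less precise. With equal SDs the variance penalty is 2/(1 + r), falling from 2.0 at r = 0 to 1.11 at r = 0.8. With unequal SDs it can vanish: at k = 0.5 and r = 0.5 both variances are 0.75. The true size is unknown because neither r nor the SDs are given.

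Two stronger conclusions do not follow. Change is not shown to be noisier than the follow-up score alone, which needs r below k/2. Nor is there bias: T0 is scored before the envelope is opened, so both approaches estimate the same between-group difference in expectation. The primary WOMAC outcome and the sample size do not rest on this point.

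**What to change.** In Section 7, state that the adherence GEE takes the scores at T1, T2, T3 and T4 as responses, with group, visit, group-by-visit and the T0 score as a covariate, and that the adjusted between-group difference with its confidence interval is reported at each visit. Letting the T0 slope differ by visit keeps the precision guarantee at each visit, since the correlation may differ between T1 and the postoperative visits. Section 6.2 may keep the word change: with T0 in the model the estimate is the same under either label.

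The cost is a sentence or two of wording and a few model terms. T0 is already collected before allocation, so no new data, visits or participants are needed.
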